### **Considerations in the handling of BLQ data for summarizing plasma PK concentration data**

BLQ values will be imputed for mean concentration-time plots and tabular summaries according to the following rules:

- All BLQ values will be set to zero, except when an individual BLQ falls between two measurable values or one or more BLQs fall at the end of a subject profile, in which case they will be set to missing;
- Mean values will be reported only if calculated on a minimum of 3 quantifiable concentrations. The number of subjects contributing to the calculation of the mean will be specified in a footnote to the mean plots (both in linear and semi-log scales) if lower than the total amount of samples available per time point;

A high proportion of BLQ values may affect derivation of SD; if more than 30% of values at a time-point are imputed, then SD will not be displayed.

Tabular summaries for concentration-time data will report N (number of subjects who received treatment), n (number of subjects with non-missing values) and, if applicable, number imputed (number of subjects with imputed values (ie, BLQ assigned zero concentration)).

### **Considerations in the handling of BLQ data for summarizing urine PK concentration data**

- For instances in which the subject did not void during the specified interval and 'NS' is present in the listing, the concentration value will be set to missing.

### **Considerations in the handling of missing data for the generation of urine PK Parameters**

- For instances in which the subject did not void during the specified interval the concentration will be set to zero to allow calculation of urine PK parameters.

#### **6.7.6.2. Pharmacokinetic Parameters Calculation Methods**

PK parameters will be calculated by non-compartmental analysis methods from the concentration-time data following these guidelines:

- Actual sampling times relative to dosing rather than nominal times will be used in the calculation of all derived PK parameters;
- There will be no imputation of missing data;
- Any subjects with missing concentration data will be included in the PK analysis set provided that at least  $C_{maxSS}$  and/or  $AUC_{0-tauss}$  can be reliably calculated. A decision will be taken on a case by case basis by the PK Scientist after consultation with the sponsor;
- $C_{max}$  and  $C_{maxSS}$  will be obtained directly from the concentration-time data;

- $t_{max}$  is the time at which  $C_{max}$  or  $C_{maxSS}$  is observed;
- $\lambda_Z$  will be estimated at terminal phase by linear regression after log-transformation of the concentrations:
  - Only those data points that are judged to describe the terminal log-linear decline will be used in the regression
  - A minimum number of three data points in the terminal phase will be used in calculation  $\lambda_Z$  with the line of regression starting at any post - $C_{max}$  data point ( $C_{max}$  should not be part of the regression slope). The adjusted correlation coefficient ( $R^2$  adjusted) in general should be greater than 0.80.
  - The interval used to determine  $\lambda_Z$  should be equal or greater than 1.5-fold the estimated half-life or otherwise flagged and used at the PK scientist's best knowledge and judgment. The corresponding estimated  $t_{1/2}$  will need to be flagged or excluded from statistical analysis accordingly.
- $t_{1/2}$  will be calculated as  $\ln 2 / \lambda_Z$ ;
- $C_{avSS}$  will be calculated as  $AUC_{0-\tau_{avSS}} / \tau_{avSS}$ ;
- $AUC_{0-\tau}$  and  $AUC_{0-\tau_{avSS}}$  will be calculated using the linear up/linear down method;
- $C_{minSS}$  will be obtained directly from the concentration-time data. In the event of a minimum concentration during the dosing interval at steady state ( $C_{minSS}$ ) not coinciding with the pre-dose concentration at steady state ( $C_{trough}$  on day 21), both parameters will be reported;
- $R_{ac}(AUC)$  will be calculated as  $AUC_{0-\tau_{avSS}} / AUC_{0-\tau}$ ;
- $R_{ac}(C_{max})$  will be calculated as  $C_{maxSS} / C_{max}$ ;
- $A_{\tau_{avSS}}$  is the cumulative amount excreted over the dosing interval and will be calculated as the sum of the products of concentration and urine volume over the appropriate collection intervals. For the calculation of urine PK parameters the protocol time intervals should be used. If a subject urinates into the toilet or a urine sample is lost any other way, or if no urine volume has been recorded for a sampling interval, the cumulative amount excreted starting with this interval cannot be calculated. If, however, a subject is unable to urinate, no amount excreted has been lost and the cumulative amount can continue to be calculated past that collection interval. For the affected time interval, the partial amount will be zero;
- $Fe\%$  is the fraction of unchanged drug in urine expressed as a percentage and will be calculated as  $Fe\% = (A_{\tau_{avSS}} / Dose) * 100$ .

If  $t_{last}$  (last time point with measurable concentration) is before 24 hour post-dose in more than

50% of treated subjects s at any particular dose of GSP 304 or Spiriva® Respimat®, AUClast (area under the plasma concentration time curve from time zero to last time point with measurable concentration) may be estimated and compared between different doses of GSP 304 and Spiriva® Respimat® by ANOVA.

Any inconsistency between plasma and urine PK would be will be further investigated and might be flagged and/or excluded from the analysis at the discretion of the PK Scientist after consultation with the sponsor.

An exploratory PK/ glomerular filtration rate (GFR) analysis of GSP304 in urine and plasma may be performed if deemed appropriate following review of the summary PK and GFR data. The decision to perform this analysis will be made by the Sponsor upon review of the tables, figures and listings produced at the end of the study. If the decision is made not to proceed with the PK/ GFR analysis, this section of the SAP will not be applicable and the outputs described herein will not be presented.

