##### **3.2.2. Secondary Endpoints**

The secondary endpoints are:

- Amount ( $A_{etau}$ ) and fraction of dose of tiotropium ( $F_e$ ) excreted in urine over the dosing interval on Day 1 and Day 21
- Peak concentrations during the dosing interval ( $C_{max}$ ) on Day 1
- Area under the plasma concentration-time curve over the dosing interval ( $AUC_{0-\tau}$ ) on Day 1

- Time of peak drug concentration over the dosing interval ( $t_{max}$ ) on Day 1 and Day 21
- Average concentration during a dosing interval at steady state ( $C_{avSS}$ ) on Day 21
- Accumulation ratio ( $R_{ac}$ )
- Change from baseline in peak  $FEV_1$  within 12 hours post-dose on Day 1 and Day 21
- Change from baseline (Day 1) at Day 21 (Week 3) in trough  $FEV_1$  response at approximately 24 hours after the last dose (average of 23 hours 15 minutes and 23 hours 45 minutes post-dose measurements), in comparison with GSP304 placebo
- Change from baseline in time-normalized area under the curve for  $FEV_1$  measured over 12 hours on Day 1 and Day 21
- Time to onset of response, defined as at least 12% and 200 mL increase in  $FEV_1$  within 12 hours of dosing on Day 1
- Time to achieving steady state as measured by  $FEV_1$  trough assessments
- Time to achieving steady state as measured by FVC trough assessments

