#### **6.5.4. Pharmacokinetic Set (PKAS)**

This will include all subjects who are randomized, received at least 1 dose of study treatment and have at least 1 quantifiable PK sample and do not have exclusionary major protocol deviations. The PKAS will be used to analyze the PK endpoints unless otherwise specified in this SAP. Major and exclusionary protocol deviations will be defined in section 7.3 and by clinical review prior to unblinding.

Subjects or data may be excluded from the PKAS at the discretion of the PK Scientist upon consultation with the sponsor. Any data excluded will be discussed in the CSR. Any excluded subject will have his or her concentration and PK parameter data (if available) listed only. Subjects who receive placebo will not be part of the PKAS. The PKAS will be used for all tables and graphical summaries of the PK data

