**Table 6: Plasma Pharmacokinetic Parameters (Day 1)**

Parameter	Definition
AUC 0-tau	Area under the concentration-time profile over the dosing interval
C max	Peak concentrations during the dosing interval
t last	Time of last quantifiable concentration
t max	Time of peak drug concentration

The PK parameters in Table 7 will be determined for Tiotropium in plasma following multiple dose administration (Day 21). The terminal elimination half-life will be reported only if data permit a reliable estimation.

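### Sections 6.5.4 and 6.7.6.2 of the SAP give conflicting PKAS membership rules, and the second, read literally, may keep valid Day 1 PK data out of the Day 1 summaries

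*SAP*

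**What the plan says.** **Membership, section 6.5.4.** The PKAS takes randomized subjects who "received at least 1 dose of study treatment and have at least 1 quantifiable PK sample" and have no exclusionary major deviation. Nothing is required on Day 21. The same definition stands in the Technical Summary Report and in the footnote to Table 14.1.2. Placebo subjects are outside the set. The section adds a discretion: "Subjects or data may be excluded from the PKAS at the discretion of the PK Scientist upon consultation with the sponsor". On the result of exclusion it says: "Any excluded subject will have his or her concentration and PK parameter data (if available) listed only". The PKAS serves all PK tables and graphical summaries.

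**Calculation rules, section 6.7.6.2.** A bullet among the non-compartmental guidelines says: "Any subjects with missing concentration data will be included in the PK analysis set provided that at least" CmaxSS and/or AUC0-tauSS can be reliably calculated. It continues: "A decision will be taken on a case by case basis by the PK Scientist after consultation with the sponsor".

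**Which day each parameter belongs to.** Table 6 (Day 1) lists Cmax, AUC0-tau, tmax and tlast. Table 7 (Day 21) lists CmaxSS and AUC0-tauSS. Section 3.2.2 makes Day 1 quantities secondary endpoints: Cmax ("Peak concentrations during the dosing interval"), AUC0-tau, tmax, and the urine amount and fraction excreted.

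**The concern.** Both sections define entry to the same set, and they disagree about subjects who have Day 1 data but no evaluable Day 21 profile. The SAP does not say which section governs. The case-by-case sentence does not settle it, because it names who decides but not on what criterion.

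The Day 1 secondary endpoints need nothing from Day 21. If section 6.7.6.2 is applied as written, whether a subject's first-dose exposure is summarized depends on something that happened after the first dose. That is selection on a post-dose event. Two programmers working from this SAP could also produce different PKAS counts, different PKAS demographics and different Day 1 tables from the same database.

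**Working it through.** **1. One subject under both rules.** Take a subject in an active arm with a complete, quantifiable Day 1 plasma and urine profile who withdraws on Day 10.

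| Step | Section 6.5.4 | Section 6.7.6.2 |
|---|---|---|
| Condition | One dose, one quantifiable sample, no exclusionary major deviation | CmaxSS and/or AUC0-tauSS reliably calculable |
| Met? | Yes | No: there is no Day 21 profile |
| In the PKAS? | Yes | No, unless the case-by-case decision says otherwise |
| Day 1 parameters | Summarized | Listed only |

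Early withdrawal does not by itself exclude the subject through the deviation route. Section 7.4 does not name it among its examples of major deviations, and section 7.9 computes compliance for early terminators only up to termination.

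**2. What is and is not affected.**
- Affected: Day 1 summaries of Cmax, AUC0-tau, tmax, Aetau and Fe; the Day 1 part of the urine dose-proportionality plot (Figure 14.2.5.2); PKAS counts and demographics.
- Not affected: the primary ANOVA on CmaxSS and AUC0-tauSS (section 8.4) and plasma dose proportionality (section 8.5), since these subjects have no Day 21 value under either rule; Rac, which divides a Day 21 value by a Day 1 value and so needs both.

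**3. The plan's own figures (section 4.3.1).** Two-sample t-test power with 28 per arm, difference 150 mL, SD 170 mL and two-sided 5% is 90.0%, as stated. Allowing for 10% dropout, 140 / 0.90 = 155.6, against 155 randomized (31 per arm). These figures are not in dispute; they supply the dropout rate and the arm size.

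**4. How many subjects.** Four active arms × 31 = 124. Suppose a fraction d leaves after the Day 1 profile and before an evaluable Day 21 profile.

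| d | Per arm, 31 × d | Four arms, 124 × d |
|---|---|---|
| 5% | 1.6 | 6.2 |
| 10% (SAP planning value) | 3.1 | 12.4 |
| 15% | 4.7 | 18.6 |

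At 10%, the 5th to 95th percentile range of a binomial count out of 124 is 7 to 18. Day 1 summaries would rest on up to 31 per arm under section 6.5.4 and on about 31 − 3 = 28 under section 6.7.6.2. The 10% row assumes that every dropout falls inside that window, so it is an upper figure at that dropout rate.

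**The case against.** The strongest reply is that exclusion is not automatic. The bullet ends in a case-by-case decision, and it sits among calculation guidelines directly after the rule against imputing missing data, so it may have been meant for gaps within a sampled profile. The rule without a Day 21 condition appears in several places, and whoever builds the population flags would probably work from those. This stands as to likelihood: exclusion is the literal default, not a certainty. It does not remove the conflict, because the bullet covers any subject with missing concentrations and carries no day qualifier.

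It can also be said that the SS suffix is used loosely, since the Day 1 shell of Table 14.2.4.1 heads its columns CmaxSS and AUC0-tauSS. But Tables 6 and 7 keep the parameters apart, and section 6.7.6.2 itself uses Cmax and CmaxSS as different quantities. If the suffix is loose, the bullet needs rewording all the more.

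A reader might infer three stronger things that the SAP does not support:
- *That every early withdrawal's Day 1 data are discarded.* The case-by-case sentence prevents that conclusion, and excluded data are still listed and must be discussed in the CSR.
- *That the Day 1 results become completer-only.* One evaluable Day 21 parameter is enough, and the Day 35 follow-up is not required.
- *That first-dose exposure is understated by a known amount.* If 3 of 31 had r times the Day 1 Cmax of the rest, the all-subject geometric mean would be r^(3/31) times that of the other 28: 1.040 for r = 1.5 and 1.069 for r = 2. A ratio below 1 reverses the sign; r = 0.5 gives 1 / 1.069 = 0.935. Nothing in the SAP supports any value of r.

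**Conclusion.** The conflict is real and should be corrected before the PKAS is fixed. Its reach is limited to descriptive Day 1 secondary endpoints, one exploratory Day 1 urine display, and set counts and demographics. No primary PK result changes, and section 8.3 plans no formal hypothesis test for the primary PK endpoints.

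The size is up to about 3 of 31 subjects per arm, or up to about 12 of 124 in the active arms. This rests on the 10% planning dropout and on all withdrawals falling between the Day 1 profile and Day 21; it is smaller if some leave outside that window. Bias arises only if withdrawal is related to exposure, and its direction cannot be told from the SAP. If the two are unrelated, the cost is lost Day 1 data.

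**What to change.** Keep the membership rule of section 6.5.4 and replace the bullet in section 6.7.6.2 with:

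> A subject with missing concentrations remains in the PKAS and contributes each PK parameter that can be reliably calculated on that day; CmaxSS and AUC0-tauSS are required only for the Day 21 analyses. Case-by-case decisions by the PK Scientist apply to individual parameters, not to PKAS membership, and lack of Day 21 data is not a reason to exclude Day 1 parameters.

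Section 6.5.4 has its own discretionary exclusion of subjects or data. A cross-reference there to the new wording would stop the same selection from returning by that route.

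The cost is one replaced bullet and a cross-reference. No new data are needed and the primary analysis is unchanged. The downside is that Day 1 and Day 21 tables will show different n, which a footnote can explain.

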#### **6.7.7. Pharmacodynamics Parameter Calculation: Time-normalized Area under the Curve (AUC) for FEV1 measured over 12 hours**

Time-normalized Area under the Curve (AUC) for FEV1 measured over 12 hours is defined as the area between baseline FEV1 and the FEV1 curve from 0 to 12 hours divided by 12 hours.

12 hour serial spirometry will be performed at Day 1 and Day 21 of each treatment period: spirometry will be performed immediately at 5 minutes ( $\pm 3$  minutes), 15 minutes ( $\pm 2$  minutes), 30 minutes ( $\pm 5$  minutes), 60 minutes, 90 minutes, and 2 hours (120 minutes); and post-dose at 4, 6, 8, 10, 12, 23 hours 15 minutes and 23 hours 45 minutes.

AUC is calculated from zero time to 12 hours (AUC0-12), using the trapezoidal method, divided by 12 hours to give the AUC0-12/12h values in litres. Non-missing FEV1 values at the following time points are required in order to calculate the normalised AUC0-12/12h: pre-dose; at least one value between 2 hours and 6 hours post-dose (inclusive); and at least one value after 6 hours post-dose. Otherwise the normalised AUC0-12/12h will be missing.

AUC0-12/12h is calculated as follows:

$$\text{AUC}_{0-12/12h} = \frac{1}{t_{11} - t_0} \sum_{i=1}^{11} \frac{(t_i - t_{i-1})(d_i + d_{i-1})}{2}$$

Where di is the spirometry value (FEV1) obtained at time ti; ti is the time (in hours) for which di is measured: t0 = 0, t1 = 0.08, t2 = 0.25, t3 = 0.5, t4 = 1, t5 = 1.5, t6 = 2, t7 = 4, t8 = 6, t9 = 8, t10 = 10 and t11 = 12. d0 is the mean of the two pre-dose values at Day 1 or Day 21.

## **6.8. Handling of Missing Data**

### **6.8.1. Missing Pharmacodynamics Endpoints**

No explicit imputation for missing pharmacodynamics endpoints will be performed for this study. If either the baseline or the post-baseline result is missing, the change from baseline is set to missing.

Section 9.6.2 describes the sensitivity analyses to be performed for the primary endpoint in handling missing data.

### **6.8.2. Missing Start and Stop Dates for Prior and Concomitant Medication**

For the purpose of inclusion in prior and/or concomitant medication tables, incomplete medication start and stop dates will be imputed as follows:

- If year and month are present and day is missing, then set day to first day of month for start date, and set day to last day of month for end date
- If year and day are present and month is missing, then set month to January for start date, and set month to December for end date
- If year is present and month and day are missing, then set month and day to January 1 for start date, and set month and day to December 31 for end date
- Completely missing date will not be imputed

The partial dates will be provided as such in the subject data listings (with the imputed dates).

When imputing a start date, ensure that the new imputed date is sensible ie is prior to the end date of prior and concomitant medications.

### **6.8.3. Missing Start and Stop Dates for Adverse Events**

Due diligence will be done to obtain accurate AE information. If all planned methods to obtain accurate AE information have failed, missing and partial AE onset and end dates will be imputed. Imputed dates will be flagged in the individual supportive subject listings. Unless otherwise specified, the following conventions will be used:

Missing and Partial AE onset dates

- If onset date is completely missing, then onset date is set to date of first dose
- If onset year is present and
  - month and day are missing:
    - If onset year = year of first dose, then set onset date to date of first dose

- If onset year < year of first dose, then set onset month and day to December 31st.
- If onset year > year of first dose, then set onset month and day to January 1st
- month is missing:
  - If onset year = year of first dose, then set onset date to date of first dose
  - If onset year < year of first dose, then set onset month to December
  - If onset year > year of first dose, then set onset month to January
- If onset month and year are present and day is missing:
  - If onset year = year of first dose and
    - onset month = month of first dose then set onset date to date of first dose
    - onset month < month of first dose then set onset date to last day of month
    - onset month > month of first dose then set onset date to 1st day of month
  - If onset year < year of first dose then set onset date to last day of month
  - If onset year > year of first dose then set onset date to 1st day of month
- For all other cases, set onset date to date of first dose

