#### Missing and Partial AE end dates

- If end date is completely missing, end date is not imputed and the AE is flagged as “ongoing”
- If year is present and
  - month and day are missing
    - If year = year of last dose, then set end date to the date of last dose
    - If year < year of last dose, then set end month and day to December 31st
    - If year > year of last dose, then set end month and day to January 1st
  - month is missing
    - If year = year of last dose, then set end date to date of last dose
    - If year < year of last dose, then set end month to December
    - If year > year of last dose, then set end month to January
- If month and year are present and day is missing:
  - If year = year of last dose and

- month = month of last dose then set day to day of last dose
- month < month of last dose then set day to last day of month
- month > month of last dose then set day to 1st day of month
  - If year < year of last dose, then set end date to last day of the month
  - If year > year of last dose, then set end date to 1st day of month
- For all other cases, set end date to date of last dose

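### Adverse event onset imputation ignores a recorded end date, so an event known to have ended before first dose is counted as treatment-emergent

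*SAP*

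**What the plan says.** SAP section 6.8.3 opens with "Unless otherwise specified, the following conventions will be used" and then gives onset rules that lead to the first-dose date in these cases:

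- Onset date wholly missing: "If onset date is completely missing, then onset date is set to date of first dose".
- Year known but month and day missing, or month missing: "If onset year = year of first dose, then set onset date to date of first dose".
- Day missing: "onset month = month of first dose then set onset date to date of first dose".
- Anything left over: "For all other cases, set onset date to date of first dose".

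None of these rules refers to the recorded end date. End dates are handled afterwards under their own sub-heading, again without comparison with onset. One of those rules is "month > month of last dose then set day to 1st day of month". Section 10.2.2, on missing onset dates, only points back to 6.8.3.

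The section just before, 6.8.2, does contain a consistency check, but for medications: "When imputing a start date, ensure that the new imputed date is sensible ie is prior to the end date of prior and concomitant medications".

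Section 10.2.1 defines TEAEs by onset or worsening after a first dose, and pre-treatment events by onset or worsening from Day -14 up to dosing. Each class has its own table (14.3.1.2 and 14.3.1.4).

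**The concern.** Events are collected throughout the study (section 4.5) and there is a two-week run-in (section 4.1), so events that began and resolved before dosing can be in the database. If the onset of such an event is incomplete, the rules can place it on the first-dose date even though the recorded end date shows that the event was already over. The result is an impossible record, with onset after end, and a wrong TEAE flag.

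This is not a missing detail. The rule is fully stated and gives a wrong answer when followed. The medication section shows that the start-before-end problem was recognised. The safeguard is absent where the imputed date decides a safety classification. What is at stake is the accuracy of the TEAE and pre-treatment event tables, not the primary endpoints.

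**Working it through.** The SAP gives no figure to reproduce here. The check is to apply the onset rules literally to example events.

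**Inputs.** Rules from 6.8.3. TEAE and pre-treatment definitions from 10.2.1. Planned arm size 31 from 4.3.1. Assumed for illustration: first dose and randomization on 20 Jun 2017, with recorded end dates before that.

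**Onset rules applied.**

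| Recorded onset | Recorded end | Imputed onset | End minus onset | On or after first dose? |
|---|---|---|---|---|
| wholly missing | 14 Jun | 20 Jun | -6 days | yes |
| 2017 only | 14 Jun | 20 Jun | -6 days | yes |
| day 8, month missing, 2017 | 14 Jun | 20 Jun | -6 days | yes |
| Jun 2017, day missing | 14 Jun | 20 Jun | -6 days | yes |
| May 2017, day missing | 20 May | 31 May | -11 days | no |

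In the first four rows the event ended six days before dosing and is dated to the first dose, so it is counted as treatment-emergent. In the last row the dates are still in the wrong order, but the event does not become a TEAE.

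**Size per subject.** One misclassified subject who has no other TEAE of that preferred term changes the arm's incidence for the term by 1/31 = 0.032, or 3.2 percentage points. In the pooled GSP304 column, with 3 × 31 = 93 subjects, the change is 1/93 = 0.011, or 1.1 points. A subject who already has a TEAE of that term changes the incidence by nothing.

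**End-date rules.** These can also produce an end before a known onset, when the end day is missing:

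- End month is the last-dose month: the end is set to the last-dose day. With first dose on 20 Jun, Day 21 is 20 Jun + 20 days = 10 Jul. Any event that began later in July and whose end is recorded only as July gets an end of 10 Jul.
- End month is after the last-dose month: the end is set to day 1. An event that began on day 10 of that month and ended in it gets an end 10 - 1 = 9 days before its onset.

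Follow-up runs two weeks past the last dose (section 4.1), so such events can occur. TEAE status depends on onset or worsening, and no table of event duration is listed in Table 12 or section 12.1, so this second fault reaches the listings only.

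**With an end-date check.** Taking the earlier of the rule's date and the recorded end date gives 14 Jun in the first four rows. By section 6.7.2 that is study day 14 - 20 = -6, inside the Day -14 window, so the event is pre-treatment. The fifth row becomes 20 May, which is 31 days before first dose (Day -31). It is neither treatment-emergent nor within the Day -14 definition.

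**The case against.** The strongest defence is that moving an unknown onset to the first dose is a usual conservative convention: it avoids understating events on treatment. That stands wherever the end date is missing or falls on or after first dose. It does not cover an event whose recorded end date shows that it was over before dosing, because there the rule overrides known data.

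Four further points limit the reach of the finding:

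- **Rarity and visibility.** Imputation is used only after attempts to obtain the date have failed, and imputed dates are flagged in listings, where the contradictory end date would also appear. This stands, although a flag in a listing does not correct a table.
- **Attribution.** A reader might infer that run-in events would be attributed to study drug. The SAP does not support that. Relatedness is the investigator's judgement (10.2.1) and date imputation does not alter it. Only the TEAE flag is wrong.
- **Frequency.** A reader might infer that the fault is common because part of the run-in often falls in the same calendar month as the first dose. Calendar overlap does not measure frequency. The fault needs an incomplete onset, an end date that precedes dosing, and failed queries, all together. The SAP gives no rate for that combination.
- **Bias between arms.** The rule is the same for every arm, and nothing in the SAP shows that it would favour one.

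The opening phrase that allows for other specification does not rescue the rule, since nothing else is specified for event onset.

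**Conclusion.** The gap is real and minor. Followed literally, section 6.8.3 turns an event known to have ended before dosing into a TEAE with an onset after its end. The number of affected events cannot be derived from the SAP and is probably small.

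The 3.2-point effect per subject assumes a safety set of exactly 31 in the arm and no other TEAE of the same term in that subject. The classification assumes that an undated-time onset on the first-dose day counts as treatment-emergent. The SAP does not say so, but this is the natural reading and the evident purpose of the rule.

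The end-date fault is lesser. It arises only when the end day is missing and the end month is the last-dose month or later. A reader might take it to affect TEAE counts, but those depend on onset or worsening.

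**What to change.** Add to section 6.8.3, to be applied before the other onset rules:

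> If the recorded end date, complete or partial, shows that the event ended before first dose, the first-dose imputation does not apply: the onset is set to the date the onset rules would otherwise give or the end date, whichever is earlier (for a partial end date, the last possible day before first dose consistent with it). The event is not treatment-emergent, and it is tabulated as a pre-treatment AE only if it meets the Day -14 definition in 10.2.1. If an imputed end date is earlier than the onset date, it is set to the onset date.

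This names the date to impute, covers partial end dates, and does not label screening-period events as pre-treatment against the SAP's own definition. The first-dose default is untouched wherever the timing is truly unknown. The cost is one short paragraph and a few lines of derivation code, with the order of steps stated, settled before database lock. No data collection or primary analysis changes.
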